## 2. Background

### Immune checkpoint inhibitors

In recent years, significant progress has been made, particularly in the areas of personalized medicine and cancer therapeutics. Immunotherapy, including adoptive cell transfer and immune checkpoint inhibitors (ICIs), harnesses the body's immune system to combat tumor cells. Both as standalone treatments and in combination with traditional therapies like radiotherapy and chemotherapy, immunotherapy has achieved notable success in treating various cancers. Coinhibitory receptors, such as programmed cell death 1 (PD-1) and cytotoxic T lymphocyte antigen

4 (CTLA-4), are expressed on T cells and negatively regulate T cell-mediated immune responses. Tumor cells exploit these receptors to induce immune tolerance and T cell exhaustion. ICIs, such as anti-CTLA-4, anti-PD-1, and anti-PD-L1 antibodies, target these receptors to reactivate the immune system against tumors. Three major groups of ICIs—PD-1 inhibitors (Nivolumab, Pembrolizumab, Cemiplimab), PD-L1 inhibitors (Atezolizumab, Durvalumab, Avelumab), and CTLA-4 inhibitors (Ipilimumab)—have been approved by the US Food and Drug Administration (FDA) for the treatment of various cancers. However, only a subset of patients (20–40%) benefit from this therapy, underscoring the need for reliable predictive biomarkers. Factors such as tumor mutational burden (TMB), PD-L1 expression, the microbiome, hypoxia, interferon-γ, extracellular matrix (ECM), and the molecular and cellular composition of the tumor microenvironment (TME) are all associated with immunotherapy outcomes.

The approval of ipilimumab in 2011 marked the beginning of ICIs as a novel treatment option, revolutionizing cancer therapy. These therapies have provided long-lasting results with relatively low toxicity in certain cases. Unlike traditional treatments, ICIs work by reactivating the immune system to combat tumor cells. Immune checkpoints regulate the balance between proinflammatory and anti-inflammatory signals in the body's immune system under normal conditions. These checkpoints are a collection of inhibitory and stimulatory pathways that control immune cell activity. In recent years, antibodies targeting immune inhibitory receptors such as CTLA-4, PD-1, and PD-L1 have become the most widely used immunotherapeutic agents.

### A standardized extract of cultured Lentinula edodes mycelia (AHCC®)

AHCC® is a standardized extract of cultured shiitake or Lentinula edodes mycelia (AHCC®) which contains a mixture of nutrients including oligosaccharides, amino acids, and minerals obtained through the liquid culture process of shiitake mycelia. It is produced by Amino Up Co., Ltd. (Sapporo, Japan) under the trademark "AHCC®." The shiitake mycelia used for AHCC® are cultured in a liquid medium where the mycelia proliferate and form globular fungal bodies but not fruiting bodies. AHCC® is produced through the unique manufacturing process of culturing the mycelia followed by separation, sterilization, and freeze-drying. The most abundant component of AHCC® is oligosaccharides which comprise about 74% of the dry weight of AHCC®.

[figure not shown]
Polysaccharides are ubiquitous among fungi from yeast to mushroom, and these compounds impart structural properties to the organisms. Although the polymeric compositions of various fungal polysaccharides are unique and specific to each organism, the structural configurations are highly conserved. Due to the ubiquitous presence of fungus in the environment and diet, mammalian immune systems have developed innate pattern recognition

systems for fungal polysaccharides. The interaction between fungal derived glucans and various cells of the immune system results in immunostimulatory effects, which in-turn prime the immune system for defense against potential invading microorganisms. The unique capacity of fungal derived glucans to act as biological response modifiers of the immune system has stimulated wide-spread research into their uses as functional foods. The immunological effects of AHCC have been investigated in numerous publications, and the product has been utilized as an immunostimulatory food for over 15 years in Japan. AHCC has been reported to improve the prognosis of patients with postoperative hepatocellular carcinoma, and improvements in the quality of life of patients with advanced liver cancer also have been reported. In studies conducted in rodents, AHCC has been shown to reduce metastasis of rat mammary adenocarcinoma, and to ameliorate the side-effects evoked by cisplatin chemotherapy in tumor-bearing mice. AHCC also may find utility against viral and microbial infections, and has been reported to increase survival in rodents following various viral and bacterial challenges.

The mechanism(s), and specific receptor mediated interaction(s) by which AHCC affects the immune system are not completely understood; however, studies in healthy subjects administered AHCC daily for a period of 4 weeks indicate that AHCC can modulate dendritic cell number and activity. Thus, the utility of AHCC in cancer subjects and in various infectious models in rodents may be mediated through its ability to stimulate dendritic cells, which are potent antigen presenting cells that are able to prime T-cells. Finally, recent evidence also has suggested that the functional properties of AHCC may be multi-factorial; in addition to direct modulation of the immune system, AHCC also has been observed to attenuate inflammation in rats with hapten-induced colitis via prebiotic effects on the colonic microflora.

## Safety profile of AHCC in preclinical model

Figure 1. Body weight changes in male rats treated orally with AHCC for 90 days.

**Table 1.** Hematology results for male and female rats following daily gavage administration of AHCC-FD for a period of 90 days.

Parameter (units)	Dose group (m	g/kg body weight	/day)						
	Male (n = 10)				Female (n = 10)				
	0	1000	3000	6000	0	1000	3000	6000	
RBC ( $\times 10^4/\mu L$ )	927.7 ± 32.5	924.4 ± 13.6	930.4 ± 25.6	910.7 ± 30.6	888.5 ± 26.0	861.5 ± 21.6	883.4 ± 32.3	864.1 ± 40.0	
Ht (%)	46.71 ± 1.07	46.54 ± 1.17	$46.82 \pm 1.02$	46.36 ± 1.44	47.36 ± 1.00	46.15 ± 1.25	46.75 ± 1.86	45.94 ± 1.79	
Hb (g/dL)	15.72 ± 0.27	$15.58 \pm 0.43$	$15.66 \pm 0.38$	15.45 ± 0.54	$16.39 \pm 0.32$	15.95 ± 0.51	16.12 ± 0.60	15.88 ± 0.59	
MCV (fL)	50.38 ± 1.33	50.37 ± 1.32	$50.33 \pm 0.80$	50.94 ± 1.61	$53.33 \pm 0.74$	53.60 ± 1.23	52.93 ± 1.03	$53.19 \pm 0.92$	
MCH (pg)	16.96 ± 0.48	$16.85 \pm 0.43$	$16.85 \pm 0.46$	16.97 ± 0.54	18.47 ± 0.29	$18.50 \pm 0.49$	18.25 ± 0.34	18.39 ± 0.43	
MCHC (g/dL)	33.65 ± 0.27	$33.49 \pm 0.30$	$33.47 \pm 0.54$	$33.34 \pm 0.29$	$34.62 \pm 0.36$	$34.56 \pm 0.35$	$34.49 \pm 0.21$	$34.57 \pm 0.49$	
WBC ( $\times 10^2/\mu$ L)	87.6 ± 16.7	87.2 ± 11.9	85.0 ± 11.4	95.7 ± 16.2	$53.0 \pm 10.0$	56.9 ± 12.8	53.8 ± 11.2	$60.8 \pm 8.0$	
Platelet count (10  /μL)	95.69 ± 10.51	$104.59 \pm 9.37$	102.11 ± 7.26	103.65 ± 11.11	103.24 ± 11.35	104.13 ± 9.37	104.98 ± 3.67	105.95 ± 11.2	
Reticulocyte count (%)	$28.0 \pm 3.1$	$28.3 \pm 2.4$	25.7 ± 1.8	$26.1 \pm 2.8$	$24.4 \pm 2.8$	$23.7 \pm 4.6$	$22.0 \pm 4.3$	$22.5 \pm 2.5$	
PT (s)	17.01 ± 1.22	16.63 ± 1.01	16.83 ± 1.17	16.33 ± 0.67	16.57 ± 0.54	16.35 ± 0.39	16.79 ± 0.55	$17.08 \pm 0.43$	
APTT (s)	25.98 ± 2.11	$24.79 \pm 1.61$	$24.91 \pm 2.07$	24.56 ± 1.83	20.06 ± 1.12	20.02 ± 1.53	20.07 ± 1.21	19.57 ± 0.87	
Differential WBC counts (%)	)								
Neutrophil (stab form)	1.60 ± 0.98	$1.24 \pm 0.72$	$2.04 \pm 0.55$	$1.08 \pm 0.91$	$1.16 \pm 0.30$	$1.36 \pm 0.43$	1.12 ± 0.77	1.32 ± 0.68	
Neutrophil (segmented)	15.00 ± 6.08	13.60 ± 3.35	16.12 ± 5.56	13.64 ± 4.02	17.52 ± 3.73	17.48 ± 5.72	18.52 ± 5.57	14.44 ± 3.03	
Eosinophil	1.48 ± 0.71	$2.00 \pm 1.80$	$2.00 \pm 1.08$	$0.96 \pm 0.63$	2.36 ± 1.12	$1.72 \pm 0.73$	$2.20 \pm 1.51$	1.24 ± 1.26	
Basophil	$0.00 \pm 0.00$	$0.00 \pm 0.00$	$0.00 \pm 0.00$	$0.00 \pm 0.00$	$0.00 \pm 0.00$	$0.00 \pm 0.00$	$0.00 \pm 0.00$	$0.00 \pm 0.00$	
Monocyte	2.36 ± 0.97	$2.40 \pm 0.88$	2.56 ± 1.18	2.12 ± 1.13	$1.88 \pm 0.96$	2.56 ± 1.38	2.12 ± 1.03	1.24 ± 0.89	
Lymphocyte	79.56 ± 7.33	80.76 ± 5.34	$77.28 \pm 6.70$	82.20 ± 4.46	77.08 ± 3.79	76.88 ± 5.79	76.04 ± 6.68	81.76 ± 3.25	
Others	$0.00 \pm 0.00$	$0.00 \pm 0.00$	$0.00 \pm 0.00$	$0.00 \pm 0.00$	$0.00 \pm 0.00$	$0.00 \pm 0.00$	$0.00 \pm 0.00$	$0.00 \pm 0.0$	

All values represent the mean ± SD.

APTT, activated partial thromboplastin time; Hb, hemoglobin; Ht, hematocrit; MCH, mean corpuscular hemoglobin; MCHC, mean corpuscular hemoglobin concentration; MCV, mean corpuscular volume; PT, prothrombin time; RBC, red blood cell count; WBC, white blood cell count.

Table 2. Urinalysis results for of male and female rats following 90-day gavage administration of AHCC-FD.

Parameters measured		Male				Female			
Dose (mg/kg body weight/day) Number of animals examined		0 10	1000 10	3000 10	6000 10	0 10	1000 10	3000 10	6000 10
рН	6.0	0	0	0	2	0	0	1	3
	6.5	0	0	2	3	0	0	3	6
	7.0	0	0	2	4	0	0	1	1
	7.5	1	1	1	0	0	3	2	0
	8.0	3	3	2	0	1	2	1	0
	8.5	6	6	3	1++	9	5	2++	0++
Protein	_	1	0	0	0	3	0	0	0
	±	1	3	0	0	5	7	4	2
	1+	8	6	6	3	2	2	4	7
	2+	0	1	4	6	0	1	2	1
	3+	0	0	0	1++	0	0	0+	0++
Glucose	_	10	10	10	10	10	10	10	10
Ketone body	_	10	10	10	10	10	10	10	10
Urobilinogen	0.1 EU/dL	10	10	10	10	10	10	10	10
Bilirubin	_	10	10	10	10	10	10	10	10
Occult blood	-	4	4	8	7	9	7	9	8
	±	3	4	2	3	0	3	1	2
	1+	1	1	0	0	0	0	0	0
	2+	2	0	0	0	1	0	0	0
	3+	0	1	0	0	0	0	0	0
Specific gravity	1.000-	0	0	0	0	0	1	0	0
	1.010								
	1.011-	0	0	0	0	0	0	0	1
	1.020								
	1.021-	1	0	0	0	2	2	2	0
	1.030								
	1.031-	7	5	3	1	4	3	3	4
	1.040								
	1.041-	1	4	4	5	2	4	3	4
	1.050								
	1.050<	1	1	3	4++	2	0	2	1
Urine volume	mL/21 h	17.05 ± 4.05	14.55 ± 2.15	14.40 ± 3.91	14.90 ± 3.44	10.35 ± 3.46	15.75 ± 13.21	12.20 ± 6.33	13.50 ± 8.8

Values are number of animals with findings.

Table 3. Results of Ames reverse mutation experiments conducted with AHCC-FD in the absence (-S9) and presence of metabolic activation (+S9).

Metabolic activation	Concentration (µg/plate)	Number of revertant colonies per plate (number in parentheses represent the mean number of colonies)												
		TA102		TA1535		TA1537	TA1537		TA100		TA104		TA98	
-S9	0 (negative control)	384		7		8		134		442		17		
		324		7		6		122		498		22		
		333	(347)	11	(8)	7	(7)	114	(123)	527	(489)	20	(20)	
	156	383		11		8		-		-		-		
		386	(385)	10	(11)	7	(8)	-		-		-		
	313	403		7		5		118		118		15		
		379	(391)	7	(7)	7	(6)	112	(115)	588	(576)	9	(12)	
	625	377		8		7		109		513		19		
		403	(390)	6	(7)	8	(8)	108	(109)	527	(520)	16	(18)	
	1250	422		9		6		118		482		15		
		411	(417)	10	(10)	5	(6)	115	(117)	535	(509)	16	(16)	
	2500	411		8		5		116		534		20		
		450	(431)	5	(7)	7	(6)	103	(110)	547	(541)	17	(19)	
	5000	461		12		11		136		550		15		
		398	(430)	7	(10)	7	(9)	130	(133)	656	(603)	24	(20)	
+S9	0 (negative control)	364		7		6		141		566		34		
	o (negative control)	402		7		10		140		605		35		
		384	(383)	9	(8)	10	(9)	130	(137)	554	(575)	40	(36)	
	156	395	(303)	13	(0)	8	(0)	-	(131)	-	(575)	-	(30)	
		402	(399)	7	(10)	12	(10)	_		_		_		
	313	424	()	7	()	7	()	150		556		29		
	-	392	(408)	11	(9)	8	(8)	140	(145)	451	(504)	25	(27)	
	625	391	()	11	(-)	8	(-)	158	()	475	()	27	()	
	020	389	(390)	8	(10)	10	(9)	151	(155)	567	(521)	32	(30)	
	1250	407	()	12	()	11	(-)	144	(100)	581	()	35	()	
	1250	390	(399)	7	(10)	10	(11)	136	(140)	522	(552)	31	(33)	
	2500	400	(333)	9	(10)	7	()	157	(1-10)	611	(332)	35	(33)	
	2500	412	(406)	6	(8)	6	(7)	136	(147)	697	(654)	28	(32)	
	5000	438	(100)	5	(0)	10	(-)	182	()	600	(00.1)	31	(32)	
	3000	415	(427)	8	(7)	12	(11)	145	(164)	548	(574)	38	(35)	
Positive Controls														
-S9	Positive control	MMC		NaN 3		9-AA		AF-2		AF-2		AF-2		
	Concentration (µg/plate)	0.05		0.5		80		0.01		0.01		0.1		
	No. of revertant colonies/plate	1297		200		194		688		1309		484		
		1343	(1320)	262	(231)	289	(242)	625	(657)	1283	(1296)	470	(477)	
+S9	Positive control	2-AA		2-AA		2-AA		2-AA		2-AA		2-AA	. ,	
	Concentration (µg/plate)	5		2		2		1		5		0.5		
	No. of revertant colonies/plate	1518		322		182		1387		3072		299		
	7	1437	(1478)	310	(316)	197	(190)	1333	(1360)	2931	(3002)	344	(322)	

AA, 2-aminoanthracene; 9-AA, 9-aminoacridine hydrochloride hydrate; AF-2, 2-{2-furyl}-3-(5-nitro-2-furyl) acrylamide; MMC, mitomycin C; NaN3, sodium azide.

### Safety profile of AHCC in phase 1 clinical trial4

**Table 4.** Lab results in 26 health volunteers

values are infinitely of aliminas with infants.

-, normal;  $\pm$ , slight; 1+, moderate; 2+, severe; 3+, very severe.

+,, significantly different from the control groups ( $p \le 0.05$ , Mann–Whitney's *U*-test).

++, significantly different from the control groups ( $p \le 0.01$ , Mann–Whitney's *U*-test).

Parameter	Baseline	Final
Systolic BP (mmHg)	112±14.8	114±15.8
Diastolic BP (mmHg)	$71 \pm 9.2$	$72 \pm 13.5$
Pulse (per min)	$73 \pm 11.1$	$76 \pm 12.3$
WBC (K/ $\mu$ L)	$7 \pm 1.7$	$7 \pm 1.4$
HCT (%)	$41 \pm 4.1$	$42 \pm 4.0$
HBG (g/dL)	$14 \pm 1.4$	$14 \pm 1.4$
Platelets (u/mL)	$259 \pm 69.3$	$269 \pm 61.4$
PT (s)	$11 \pm 0.5$	$10 \pm 0.5$
PTT (s)	$29 \pm 1.5$	$28 \pm 1.4$
TSH (mL IU/L)	$2 \pm 0.8$	$2 \pm 1.0$
BUN (mg/dL)	$15 \pm 4.3$	$14 \pm 4.6$
Creatinine (mg/dL)	$1 \pm 0.1$	$1 \pm 0.1$
Ca (mg/dL)	$9\pm0.4$	$9\pm0.4$
Mg (mg/dL)	$2 \pm 0.1$	$2 \pm 0.1$
Glucose (mg/dL)	$5 \pm 13.5$	$84 \pm 10.3$
Na (mmol/L)	$139 \pm 1.7$	$139 \pm 1.9$
K (mmol/L)	$4\pm0.3$	$4\pm0.2$
Cl (mmol/L)	$104 \pm 1.9$	$103 \pm 1.6$
CO 2 (mmol/L)	$24 \pm 2.0$	$24 \pm 2.3$
Amylase (U/L)	$50 \pm 13.6$	$51 \pm 16.4$
Lipase (U/dL)	$38 \pm 10.5$	$37 \pm 10.6$
ALT (U/L)	$19 \pm 5.8$	$22 \pm 9.1$
AST (U/L)	$21 \pm 8.8$	$23 \pm 12.5$
ALK PHOS (U/L)	$64 \pm 20.3$	$64 \pm 18.0$
Urine analysis	normal	normal
EKG	normal	normal

## 3. Study objectives

### **Primary objective:**

• To investigate whether add-on of AHCC can enhance the effect of immunotherapy in cancer patients.

### **Secondary objectives**:

- To evaluate the progression-free survival of patients who receive AHCC along with immunotherapy.
- To evaluate the overall survival of patients who receive AHCC along with immunotherapy.
- To evaluate the safety profile in cancer patients who receive AHCC along with immunotherapy.
- To evaluate the Quality of life in patients who receive AHCC along with immunotherapy.

# 4. Study design.

This is a prospective double-blind, randomized, placebo-controlled trial.

### 5. Patient selection

- 6.1 Inclusion criteria
  - 6.1.1 Liver cancer patient who will receive immunotherapy
  - 6.1.2 At least one measurable tumor, according to RECIST version 1.1, that has not been treated with any local procedure.
  - 6.1.3 Age  $\geq$  20 years old.
  - 6.1.4 ECOG performance status 0 or 1.
  - 6.1.5 White blood count  $\geq$  2,000/ $\mu$ L; platelet count  $\geq$  60,000/ $\mu$ L.
  - 6.1.6 Liver transaminases (ALT and AST)  $\leq$  5 times upper limit of normal values (ULN); total bilirubin  $\leq$  2 times ULN; creatinine clearance or eGFR > 50 mL/min (either Cockcroft-Gault or MDRD is acceptable, whichever is higher).
  - 6.1.7 Subjects with chronic hepatitis B virus infection (HBV surface antigen (HBsAg) positive) must start antiviral therapy with nucleoside analogs (e.g., entecavir or tenofovir, according to current practice guidelines) before start of study drug treatment .

### 6.2. Exclusion criteria

- 5.2.1 Major systemic diseases that the investigator considers inappropriate for participation.
- 5.2.2 Any active autoimmune disease or history of known autoimmune disease except for vitiligo, resolved childhood asthma/atopy, type I diabetes mellitus, residual hypothyroidism due to autoimmune condition only requiring hormone replacement, psoriasis not requiring systemic treatment, or conditions not expected to recur in the absence of an external trigger are permitted to enroll.
- 5.2.3 Dementia or significantly altered mental status that would prohibit the understanding or rendering of informed consent and compliance with the requirements of this protocol.
- 5.2.4 Prior therapy with an anti-PD-1, anti-PD-L1, or anti-CTLA-4 antibody (or any other antibody or drug specifically targeting T-cell costimulation or checkpoint pathways).
- 5.2.5 Requirement of systemic treatment with either corticosteroids (> 10 mg daily prednisone equivalents) or other immunosuppressive medications within 14 days of study drug administration. Inhaled or topical steroids and adrenal replacement doses > 10 mg daily prednisone equivalents are permitted in the absence of active autoimmune disease.
- 5.2.6 Prior organ allograft or allogeneic bone marrow transplantation.
- 5.2.7 Other severe acute or chronic medical or psychiatric condition, or laboratory abnormality that may increase the risk associated with study participation and in the judgment of the investigator would make the patient inappropriate for entry into this study.

# 6. Screening and registration

- 6.1 The following examinations must be done to check the patients' eligibility:
  - 7.1.1. Tumor assessment (according to RECIST 1.1); histological proof of HCC; viral hepatitis serology (HBsAg, anti-HBs, anti-HCV), HBV DNA level (for HBsAg (+) or anti-HBc (+) subjects), HCV RNA level (for anti-HCV (+) subjects).

- 7.1.2. Within 1 week of registration: physical examination (including performance status), hematology/ biochemistry.
- 6.2 The following procedures must be done and data recorded at registration: written informed consent, demography, medical history, tumor staging (BCLC, AJCC), tumor assessment (according to RECIST 1.1), Child-Pugh score, hematology/biochemistry, viral hepatitis status.

## 7. Treatment and follow-up plan

- 7.1 All enrolled patients will receive AHCC or placebo 3g every day until disease progression, intolerance or patient or physician decision to discontinue.
- 7.2 During treatment the subjects will be followed according to the follow-up plan summarized in the following table:
  - 7.2.1 Hematology and biochemistry levels will be checked within 72 hours before each administration of study drug treatment.
  - 7.2.2 A window of +/- 7 calendar days is allowable for imaging examination for tumor assessment.
  - 7.3 Prohibited treatment during the study drug treatment period includes the following:
    - 7.3.1 Investigational agents for the treatment of cancer;

7.3.2 Systemic steroids > 10 mg within 14 days of dosing (with a few exceptions eg, steroids for adrenal insufficiency, steroids if taken as part of prophylaxis for CT prep).

	Screen	Treatment Cycles (21-day cycles)					End-of-treatment
	Screen						(EOT) evaluation a
		C1 C2		C3	C4	C5	4 weeks after last
Week		C6	C7	C8	C9	C10	treatment
		:	:	:	:	:	treatment
Informed consent	Х						
Inclusion/exclusion criteria	Х						
Demography/ tumour staging	X						
Medical history	X						
Vital signs	X	Х	Х	Х	Х	Х	X
ECG	X						X
Blood test b	Х		Х	Х	Χ	Χ	Х
Urinalysis	Х					Х	X
HBV/HCV serology markers c	Х						Х
Performance status	Х	Х	Х	Х	Χ	Х	X
Chest X-ray	Х						X
Tumor assessment d	Х					Χ	
Treatment		Х	Х	Х	Х	Х	
Pregnancy test e	Х						
lmmunological study f	Х					Х	Х
Thyroid function g	Х						Х
Tolerability/AE reporting		Χ	Χ	Χ	Х	Х	Х
QOL questionnaire	Х			Х		Χ	Х

- a) The EOT assessment will take place at approximately 1 month after last treatment.
- b) Blood tests will include CBC/DC, albumin, total and direct bilirubin, transaminases (AST and ALT), ALP, AC sugar, sodium, blood urea nitrogen (BUN), creatinine, amylase, lipase, Troponin-T(or hs-cTnT), pro-BNP (brain natriuretic peptide), and creatinine kinase (CK) or CK-MB isoform (CK-MB). Other biochemistry tests may be done at the discretion of individual investigators.
- c) HBV and HCV serology markers, including HBsAg, anti-HBs, anti-HBs, and anti-HCV, will be checked at baseline only. Subjects who test positive for HBsAg are categorized as chronic HBV infection. Subjects who test positive for anti-HCV are categorized as chronic HCV infection. For subjects with chronic HBV infection, HBV DNA levels should be checked at baseline and at EOT evaluation. For subjects with chronic HCV infection, HCV RNA levels should be checked at baseline and at EOT evaluation.
- d) Tumor assessment (according to RECIST 1.1) will be done every 12 weeks. Computed tomography is the preferred imaging modality and should include imaging of chest and abdomen at baseline and follow-up.
- e) For women with childbearing potential.
- f) In brief, 20ml blood and tumor sample will be collected. Please refer to Sec. 10 for detailed description for collection of each type of samples.
- g) Including serum T3, T4 and TSH.
- h) Quality of life is assessed using the EORTC QLQ-C30 and QLQ-HCC18 at baseline, every 6 weeks and EOT.

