Following the Screening period to confirm eligibility, 98 study participants, who meet the entry criteria, will be 1:1 randomized to study intervention (3g of AHCC oral per day or matching placebo) and will be stratified by AFP (<400 vs. ≥400). Enrollment is anticipated to be completed within 2 years, with each participant followed for 6 months since treatment. Therefore, the total duration of the study is expected to be approximately 2.5 years from the time of Institutional Review Board approval. All enrolled participants will receive AHCC or placebo 3g per day until disease progression, intolerance or patient or physician decision to discontinue. Tumor tissue and peripheral blood samples will be collected from all participants for biomarker analysis.

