Nephritis	Creatinine > 1X ULN and ≤1.5 X baseline; proteinuria 1+, <1.0g / 24 h:  • Monitor renal function weekly; hydration	Creatinine > 1.5–3.0 X baseline; proteinuria 2+, 1.0– 3.4 g/24 h: • Steroid treatment (e.g., prednisolone 0.5–1 mg/kg/day or IV equivalent) • Delay study drug administration. Monitor renal function every 2-3 days; If worsens, manage as per grade 3 • Exclude non-immune causes	Creatinine > 3.0 X baseline to ≤ 6X ULN; proteinuria ≥ 3.5 g/24 h:  • As per Grade 2  • Consider renal biopsy  • If elevations persist > 7 days or worsens, manage as per grade 4	Creatinine > 6.0 X ULN:  • Steroid treatment (e.g., prednisolone 1–2 mg/kg/day or IV equivalent)  • Consider renal biopsy • Discontinue study drug treatment
Skin rash	<10% BSA:	10–30% BSA:	>30% BSA:	Life threatening

Antihistamines and topical steroid for pruritus	
 
As per G1 if tolerable
 
If intolerable, steroid treatment (eg prednisolone 0.5–1 mg/kg/day with a 1–2 week wean)
 
Delay study drug treatment until G1 and steroids <10 mg/day
 
Consider skin biopsy if symptoms persist or recur
 
	
 
Consult dermatologist and consider skin biopsy
 
Steroid treatment (e.g., prednisolone 1 mg/kg/day or IV equivalent).
 
Delay study drug treatment until G1 and steroids <10 mg/day
 
	consequences • As per Grade 3.
---	---	--	--------------------------------

- 8.2.4 When irAE improved to Grade 1 after steroid treatment, may taper steroid dosage over at least 1 month.
- 8.2.5 For other grade 3-4 toxicities (according to CTCAE version 4) that are considered to be related to study drug treatment, study drug treatment should be held if the toxicities last for 3 days or more under best supportive care. Further study drug treatment may be considered when toxicity has resolved to ≤ grade 1, after discussion with the principal investigator.
- 8.2.6 Recent review of irAE indicated the clinical significance of the rare but potentially fatal cardiac toxicity for patients who received combination immunotherapy . Cardiac exam (echocardiography or radionuclide ventriculography (MUGA scan)) will be done at baseline, at the first imaging assessment, and at the end-of-treatment (EOT) evaluation. Troponin-T(or hs-cTnT), pro-BNP (brain natriuretic peptide), and creatinine kinase (CK) or CK-MB isoform (CK-MB) will be checked every 3 weeks before each administration of study drug treatment and at EOT evaluation.

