## 10. Criteria for discontinuation of study drug treatment

Discontinuation of study drug treatment is when a patient no longer receives study drug but continues to be followed up for tumor status and survival according to local treatment guidelines for up to half year, unless consent is withdrawn. Patients may be discontinued from study drug treatment and assessments at any time. When study drug treatment is discontinued due to the reasons listed below, no further AHCC/placebo treatment will be provided by this study and further anticancer therapy will be decided by the investigators according to current treatment guidelines. Specific reasons for discontinuation of study drug treatment include:

- 10.1 Voluntary discontinuation by the subject who is at any time free to discontinue his/her participation in this study, without prejudice to further treatment.
- 10.2 When the investigator(s) consider other treatment modalities (surgery, others) are more suitable for the subjects according to assessment of tumor response specified in the protocol.
- 10.3 Safety reasons as judged by the investigator. Severe non-compliance to protocol as judged by the investigator.
- 10.4 Incorrect enrollment, in the opinion of the investigator or study delivery team physician, which will compromise the patient's health if study drug treatment or assessments are continued.
- 10.5 Dose delay or interruption of study drug treatment for more than 3 weeks.

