- 11.4 The primary endpoint analysis and other secondary endpoints will be based on the intent-to-treat population and per-protocol population, while the safety data will be summarized based on the intent-to-treat population.
  - 11.4.1 Intent-to-treat population refers to all enrolled patients regardless of their compliance with the study drug treatment.
- 11.4.2 Per-protocol population refers to all patients who have received at least 6 weeks (2 cycles) of study medication and received the first scheduled assessment of tumor response.
  - 11.5 Disease stabilization rate (complete response + partial response by RECIST + stable disease by RECIST that last for  $\geq 8$  weeks), objective response rate (complete response + partial

- response by RECIST), and down-staging rate will be calculated with their 95% confidence intervals.
- 11.6 Progression-free survival, time-to-tumor progression, and overall survival will be calculated by the Kaplan-Meier method.
- 11.6.1 Progression-free survival is defined as the duration from the date of the first dose of study drug treatment to the date of documented disease progression or death of any cause.
- 11.6.2 Time-to-tumor progression is defined as the duration from the date of the first dose of study drug treatment to the date of documented tumor progression by imaging studies.
- 11.6.3 Overall survival is defined as the duration from the date of the first dose of study drug treatment to the date of death of any cause.
  - 11.7 The baseline and changes in immune-related biomarkers after study drug treatment will be correlated with the patients' treatment outcome, including disease stabilization, best radiographic response, time to tumor progression, progression-free survival, and overall survival.
  - 11.8 For the endpoint of the safety assessment, the tabulations will count the number of subjects reporting individual adverse events. Incidence of adverse events and serious adverse events will be summarized.
  - 11.9 The demographic features of the subjects will be summarized by descriptive statistics. Comparison between sub-groups, for examples, subjects with vs. without objective tumor response/AFP response/disease stabilization subjects with vs. without surgery after study drug treatment by using Mann-Whitney tests/ one-way ANOVA (continuous variables) or chisquare/Fisher's Exact tests (categorical variables).

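### The term study drug denotes a daily oral product in 7.1 and 10 but fits only a roughly three-weekly product in 7.2.1 and 8.2.6, so the laboratory rule conflicts with the schedule and the irAE hold and stop orders do not identify their agent

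*Protocol*

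**What the plan says.** **Daily product.** Protocol 7.1 reads: "All enrolled patients will receive AHCC or placebo 3g every day until disease progression, intolerance or patient or physician decision to discontinue". The Abstract describes the randomized intervention in the same way, as 3 g per day by mouth. Section 10 ties study drug to this product: once study drug treatment is discontinued, "no further AHCC/placebo treatment will be provided by this study", and further anticancer therapy is left to the investigators.

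**Rules tied to single administrations.** Under 7.2.1, "Hematology and biochemistry levels will be checked within 72 hours before each administration of study drug treatment". Under 8.2.6, troponin, pro-BNP and CK or CK-MB "will be checked every 3 weeks before each administration of study drug treatment and at EOT evaluation".

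**Schedule.** The table in Section 7 runs in 21-day cycles, with at most one blood test in each cycle column. Footnote b counts the same cardiac markers among the blood tests.

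**Safety orders.** The irAE table in 8.2 directs sites to delay or discontinue study drug by type and grade of event (for example, hepatitis, enterocolitis and pneumonitis at grade 3). Item 8.2.5 adds a hold rule for other related grade 3-4 toxicities. None of these instructions names AHCC/placebo or a checkpoint inhibitor.

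**Background treatment.** The first inclusion criterion in Section 5 requires that the patient will receive immunotherapy. The protocol names no agent or schedule for it.

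**The concern.** Two products are in play for every participant: a blinded oral product taken daily, and an immunotherapy given as background care. The protocol uses one undefined term, study drug, in places where the timing fits the first and in places where it does not. Two things follow.

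First, the laboratory rule cannot be carried out as written alongside daily dosing and the visit table. A site must set one of them aside, and a monitor could cite a deviation whichever it chose.

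Second, the same term carries the instructions to delay or stop treatment after an immune-related event. Read with Section 10, those orders reach only AHCC/placebo, and the text is then silent on what happens to the immunotherapy. Read with 8.2.6, which sits in the same part of the protocol, they reach a product given every 3 weeks. A site could hold the oral product, the immunotherapy or both, and point to the text each time. What is at stake is uniform handling of a safety instruction, and hence exposure to both products across sites.

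**Working it through.** **Inputs**

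- Dosing interval of AHCC/placebo: 1 day (Abstract; 7.1).
- Laboratory window: 72 hours before each administration (7.2.1).
- Cycle length: 21 days (schedule table, Section 7).
- Blood tests scheduled: at most 1 per cycle (same table).
- Interval stated for cardiac markers before each administration: 3 weeks (8.2.6).

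**Step 1. Reading study drug as the daily product.** One blood draw satisfies 7.2.1 for every dose taken in the following 72 hours. With one dose per day that is 72 / 24 = 3 doses, or 4 if the draw is made just before a dose (doses at 0, 24, 48 and 72 hours).

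- Draws needed per cycle, lower end: 21 / 4 = 5.25, rounded up to 6.
- Draws needed per cycle, upper end: 21 / 3 = 7.
- Draws scheduled per cycle: at most 1.
- Doses covered by one draw: 3/21 = 14% to 4/21 = 19%.

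So 7.2.1 would be unmet for at least 17 of the 21 doses in a cycle.

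**Step 2. Reading study drug as a product given once per 21-day cycle.** There is one administration per cycle, so one draw in the 72 hours before it is enough. That agrees with one test per cycle in the table and with the interval in 8.2.6. It does not agree with 7.1 or with Section 10.

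**Step 3. Passages side by side**

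| Place | Interval or product stated | Fits daily AHCC/placebo? | Fits one administration per cycle? |
|---|---|---|---|
| 7.1 | every day | yes | no |
| Section 10 | AHCC/placebo | yes | no (daily by 7.1) |
| 7.2.1 with the schedule table | 72 hours before each administration; at most 1 test per 21 days | no | yes |
| 8.2.6 | 3 weeks, before each administration | no | yes |
| irAE table and 8.2.5 | study drug only, no interval | not determined | not determined |

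Neither reading satisfies all of the first four rows.

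**Step 4. The irAE orders.** These carry no interval, so timing cannot settle the agent. Section 10 points to AHCC/placebo. Item 8.2.6, under the same heading as the irAE table, uses the term in a way that does not fit AHCC/placebo. No passage says what is done with the immunotherapy when an order to delay or discontinue applies.

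**The case against.** The strongest reply is that the agent is largely identified. The Abstract names AHCC or placebo as the intervention, Section 10 equates study drug with it, and immunotherapy is never called study drug. On this view 7.2.1 and 8.2.6 contain loose wording, not a second definition. Moreover, 7.2.1 states no interval of its own. It sits under 7.2, which sends the reader to the table, and the table and 8.2.6 both work in three-week steps, so a site would in practice test once per cycle.

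Much of this stands. No passage describes a three-weekly study drug. A reader might infer that in Section 8 the term simply means the checkpoint inhibitor, but the documents do not say so, and wording that fails to fit daily dosing is not a definition of something else. It is also fair that few sites would draw blood every three days. But the reply does not remove the conflict: following the table still means departing from 7.2.1 as written if study drug is taken daily. Nor does it help with the irAE orders. If study drug there means AHCC/placebo alone, the protocol leaves the immunotherapy unaddressed at each of those orders, and 8.2.6 gives a site grounds to read the term otherwise.

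Four stronger readings are tempting and are not supported.

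- **Per-protocol population.** A reader might infer that 11.4.2 is equally unclear. It asks that patients "have received at least 6 weeks (2 cycles) of study medication". That is a duration: 6 × 7 / 21 = 2 cycles, exactly as stated, and study medication most naturally means AHCC/placebo.
- **Toxicity endpoint.** A reader might infer that it is distorted. It is a binary patient outcome compared between blinded arms (11.3.1), and nothing in the documents shows how the wording would change that comparison.
- **A fixed seven-fold discrepancy in testing.** Seven is only the upper end of 6 to 7, and it sets a literal reading against the schedule.
- **The 36% and 57% rates.** A reader might take these as the share of patients affected. They are design assumptions for all grade 3/4 toxicity, not rates of the listed irAEs, and some delay orders already apply at grade 2.

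**Conclusion.** The point holds as an inconsistency in terminology that reaches safety instructions. Sections 7.1 and 10 cannot be reconciled with 7.2.1, 8.2.6 and the schedule table under a single meaning of study drug. For the laboratory rule, the gap is about 6 to 7 tests per cycle against at most 1. This assumes one dose each day and a literal 72-hour window. For the irAE orders no number can be given: the documents state neither how often those events are expected nor which agent is meant. The finding there is that one written order can be applied to different agents.

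The BOP2 stopping boundaries, the sample size and the per-protocol definition are not affected. An amendment should make the correction, because the ambiguity sits in hold and stop instructions and is cheap to remove.

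**What to change.** Add two defined terms, one for AHCC/placebo and one for the background immunotherapy. Then go through 7.1, 7.2.1, the schedule table, the irAE table, 8.2.5, 8.2.6 and Section 10, and reconcile them so that each laboratory, hold and stop instruction names the agent or agents it applies to. Item 7.2.1 and the table should also be brought to one laboratory timing that can be followed. Which rule applies to which agent, and which laboratory timing is intended, is for the sponsor and investigators to decide; this review proposes neither.

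The cost is wording in a protocol amendment, with its ethics submission. No recalculation of the design is needed.
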